18.2. EFFECTIVENESS ANALYSES

All co-primary effectiveness endpoints need to be achieved to claim overall effectiveness success. Therefore no multiplicity adjustment is necessary for primary effectiveness endpoints. The secondary effectiveness endpoint will be tested after the primary effectiveness endpoints have been achieved. The secondary effectiveness endpoint needs to be achieved to support the astigmatism tolerance claim. For the primary effectiveness endpoints, the primary analysis population will be the ITT analysis population. For the secondary effectiveness endpoint, the primary analysis population will be a mITT analysis population. The PP analysis population will also be used on the key effectiveness endpoints to support the primary ITT analyses.

18.2.1. CO-PRIMARY EFFECTIVENESS ENDPOINTS

- 1. Binocular uncorrected intermediate visual acuity (UCIVA) (at 6 months):
 - a. The mean acuity from the test group is statistically superior to the mean acuity from the control group. The comparison between test and control groups for mean binocular UCIVA (logMAR) will be performed using a two-sample t-test at $\alpha = 0.05$ (two-sided). The null hypothesis is that the mean acuity for the test group is greater (i.e., worse) than or equal to that for the control group. The alternative hypothesis is

that the mean for the test group is less (i.e., better) than that for the control group. Formally put as follows:

$$\begin{aligned} &H_0: \mu_T \geq \mu_C \\ &H_A: \mu_T < \mu_C \end{aligned}$$

Where μ_T is the mean logMAR acuity from the IC-8 test group and μ_C is the mean logMAR acuity from the control group.

The statistical success criterion is when H_0 is rejected by a p-value less than 0.05, demonstrating the mean binocular UCIVA from the test group is statistically superior to the mean binocular UCIVA from the control group.

- b. At least 50% of test subjects achieve 0.1 or better logMAR and at least 25% higher than the control subjects [clinical success criteria].
- 2. Binocular uncorrected near visual acuity (UCNVA) (at 6 months):
 - a. The mean acuity from the test group is statistically superior to the mean acuity from the control group. The comparison between test and control groups for mean binocular UCNVA (logMAR) will be performed using a two-sample t-test at $\alpha = 0.05$ (two-sided). The null hypothesis is that the mean acuity for the test group is greater (i.e. worse) than or equal to that for the control group. The alternative hypothesis is that the mean for the test group is less (i.e. better) than that for the control group. Formally put as follows:

$$\begin{aligned} &H_0: \mu_T \geq \mu_C \\ &H_A: \mu_T < \mu_C \end{aligned}$$

Where μ_T is the mean logMAR acuity from the IC-8 test group and μ_C is the mean logMAR acuity from the control group.

The statistical success criterion is when H_0 is rejected by a p-value less than 0.05, demonstrating the mean binocular UCNVA from the test group is statistically superior to the mean binocular UCNVA from the control group.

- b. At least 50% of test subjects achieve 0.3 or better logMAR and at least 25% higher than the control subjects [clinical success criteria].
- 3. Binocular uncorrected distance visual acuity (UCDVA) (at 6 months):
 - a. The mean acuity from the test group is non-inferior to the mean acuity from the control group using a margin of 0.1 logMAR. The comparison between test and control groups for mean binocular UCDVA (logMAR) will be performed using a t-test for non-inferiority at $\alpha = 0.05$ (one-sided). The null hypothesis is that the mean acuity for the test group is inferior to the control group by 0.1 logMAR or more. The alternative hypothesis is that the mean acuity for the test group by less than 0.1 logMAR. Formally put as follows:

$$\begin{split} &H_0{:}\,\mu_T-\mu_C\geq 0.1\\ &H_A{:}\,\mu_T-\mu_C<0.1 \end{split}$$

Where μ_T is the mean logMAR acuity from the IC-8 test group and μ_C is the mean logMAR acuity from the control group.

The statistical success criterion is when H_0 is rejected by a p-value less than 0.05, demonstrating the mean binocular UCDVA from the test group is statistically non-inferior to the mean binocular UCDVA from the control group using a margin of 0.1 logMAR.

- b. At least 50% of test subjects achieve 0.1 or better logMAR [clinical success criteria].
- 4. Monocular distance-corrected intermediate visual acuity (DCIVA) of the IC-8 IOL eyes (at 6 months):
 - a. The mean acuity of the IC-8 IOL eyes is statistically superior to the fellow control eyes in the test group. The comparison between IC-8 IOL eyes and fellow eyes in the test group for mean monocular DCIVA (logMAR) will be performed using a two-sample t-test at $\alpha = 0.05$ (two-sided). The null hypothesis is that the mean acuity for the IC-8 IOL eyes is greater (i.e., worse) than or equal to that for the fellow eyes. The alternative hypothesis is that the mean for the IC-8 IOL eyes is less (i.e., better) than that for the fellow eyes. Formally put as follows:

$$H_0: \mu_T \ge \mu_C$$
$$H_A: \mu_T < \mu_C$$

Where μ_T is the mean logMAR acuity from the IC-8 eyes and μ_C is the mean acuity from the fellow eyes.

The statistical success criterion is when H_0 is rejected by a p-value less than 0.05, demonstrating the mean DCIVA from IC-8 eyes is statistically superior to the mean DCIVA from the control eyes.

- b. At least 50% of IC-8 IOL eyes should achieve DCIVA of logMAR 0.2 or better [clinical success criteria].
- 5. Monocular photopic distance-corrected depth of defocus (measure only negative direction from zero) of the IC-8 IOL eyes (at 3 months):
 - The mean depth of focus from IC-8 IOL eyes is at least 0.5 D greater than the mean from the fellow control eyes at 0.2 logMAR visual acuity threshold [clinical success criteria]. There is no specific statistical success criterion.

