For mean binocular uncorrected visual acuities, mean values between IOL groups will be compared using two-sample t-tests. For mean monocular distance-corrected intermediate visual acuity, mean values between the eyes implanted with the IC-8 IOL and the fellow eyes in the test arm will be compared using two-sample t-tests. For monocular photopic distance-corrected defocus curve, the mean depth of focus from IC-8 IOL eyes will be numerically compared to the mean from the fellow control eyes at 0.2 logMAR visual acuity threshold. For tolerance to preoperative corneal astigmatism in IC-8 IOL eyes, postoperative monocular mean UCDVA in the eyes with 1.0 D to 1.5 D of preoperative corneal astigmatism will be compared to the postoperative mean acuity in the eyes with < 1.0 D of preoperative corneal astigmatism in a non-inferiority test. Safety data on adverse events will be compared to the historical control safety and performance endpoints (SPE) rates in Table B.2 of ISO 11979-7:2014, *Ophthalmic implants - Intraocular lenses - Part 7: Clinical investigations Safety and Performance Endpoint.* Mean monocular best-corrected distance visual acuity will be compared between the IC-8 IOL eyes and the fellow eyes in the test arm using a non-inferiority test. Rate of removals due to visual/optical reasons in the IC-8 IOL eyes will be assessed to be less than 3.1%.

VISITS AND PROCEDURES:

A comprehensive eye examination will be performed preoperatively and postoperatively. The preoperative visit will include an assessment of patient qualifications for the initial inclusion of both eyes in the study according to the protocol inclusion/exclusion criteria. The Informed Consent Form (ICF) must be signed by those patients agreeing to participate prior to any study-specific procedures being performed.

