18.0 DATA ANALYSIS METHODS

This section (section 18.0 through 18.4) highlights the key statistical methods and analyses planned for this study. The SAP includes details for all statistical methods, plans, adverse events reporting methods, and sample size calculations for the study.

Some key data and analysis conventions include the following:

For the primary and secondary effectiveness endpoints, the six-month postoperative visit will be the primary analysis time point unless otherwise noted. For the primary safety endpoints, the 12-month study visit will be the primary analysis time point.

Binocular safety and effectiveness analyses will compare the test group and the control group. Monocular safety and effectiveness analyses will compare the IC-8 IOL eyes and the monofocal fellow eyes within the test group. All co-primary effectiveness and safety endpoints have to be met to claim overall effectiveness and safety success. There is one secondary effectiveness endpoint regarding the tolerance to astigmatism in IC-8 IOL eyes, and this endpoint will only be tested when all co-primary effectiveness endpoints have been achieved. Under this plan, type I error rates will be controlled at a significance level of 0.05 per individual hypothesis without adjustment for multiplicity under any family. Other statistical comparisons in the additional analyses and supportive analyses should not be used for the purpose of claims.

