For all key safety endpoints, the primary analysis population will be the safety analysis population. The safety population will consist of all subjects who complete enrollment and have been bilaterally implanted and those subjects not successfully implanted with the IC-8 IOL but for whom the IC-8 IOL touched the eye. Safety analyses will only include available data at the time of analysis (i.e., no data imputation). Reporting of cumulative complications (occurring at any time postoperative) will include data from all subjects in the safety population. Test subjects who have undergone the IC-8 IOL surgery with attempted but failed implantation will be followed until all ocular adverse events are resolved or stable before being exited from the study, and they will be counted in the safety population.

The safety population (with no imputation) will also be used for reporting of other postoperatively measured clinical parameters that are not discussed as part of the key effectiveness or safety endpoints.

The primary reporting will be on IC-8 IOL eyes and fellow eyes in the test group or binocular outcomes from both test and control groups. However, key data such as visual acuity, refractive error, medical/lens complications and adverse events will also be reported separately for first and second eyes in the control group.

Besides the ITT (or mITT) and PP populations, key effectiveness outcomes and key safety outcome of BCDVA may also be reported for best-case subjects where appropriate. A best-case subject is defined in ISO 11979-1:2012 as a subject with no preoperative ocular pathology, no macular degeneration detected at any time, and no previous surgery for the correction of refractive errors. In this study, a best-case subject should also have no significant macular pathology at any time. Both eyes must meet the best-case criteria for inclusion in the best-case analysis.

Subjects who are disqualified prior to second-eye implantation will not be counted toward the study cohort or any analysis population. For the disqualified subjects, a listing of UCDVA and BCDVA at preoperative and before study exit will be tabulated, as well as any adverse events; no other analysis will be performed.

In addition to the above analysis populations, additional best-case analyses and exploratory subgroup analyses may also be performed as specified in the SAP.

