18.2.4. ADDITIONAL EFFECTIVENESS ANALYSES

1. Compare mean monocular uncorrected distance (UCDVA), intermediate (UCIVA) and near (UCNVA) visual acuity of the IC-8 eyes to the fellow control eyes.

- 2. Binocular +0.75 D Distance Corrected Visual Acuity compared between the test group and the control group: +0.75 D distance correction will be achieved by correcting all eyes in both groups with their best distance-corrected refraction and then placing a +0.75 D lens in front of the IC-8 IOL eyes in the test group and in front of the second eyes in the monofocal control group.
 - Binocular +0.75 D Distance Corrected Intermediate Visual Acuity (+0.75 DCIVA): Proportion of subjects achieving 20/25 or better in the test group is at least 25% more than the control group.
 - Binocular +0.75 D Distance Corrected Near Visual Acuity (+0.75 DCNVA): Proportion of subjects achieving 20/40 or better in the test group is at least 25% more than the control group.
 - c. Binocular +0.75 D Distance Corrected Distance Visual Acuity (+0.75 DCDVA): Proportion of subjects achieving 20/25 or better in the test group is not less than the control group by more than 10%.
 - d. The monocular visual acuities from the IC-8 IOL eyes in the test group will be similarly compared to the second eyes in the control group.
- 3. Supportive analyses:
 - a. The monocular co-primary endpoint analyses on DCIVA and depth of focus will be repeated by comparing IC-8 IOL eyes to the second eyes in the control group to support the primary endpoint analyses.
 - b. The co-primary endpoint analyses on binocular UCDVA, UCIVA, UCNVA and monocular DCIVA will be repeated at 12 months to support the primary endpoint analyses performed at 6 months.
 - c. The secondary endpoint on tolerance to astigmatism in IC-8 IOL eyes is repeated on the postoperative refractive cylinder with the same grouping and test to support the results from preoperative corneal astigmatism and to check the influence from postoperative refractive cylinder on the effectiveness of the device.

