18.3.1. CO-PRIMARY SAFETY ENDPOINTS

- 1. Monocular BCDVA in the IC-8 IOL eyes (at 12 months):
 - a. The mean BCDVA from the IC-8 IOL eyes is non-inferior to that from the fellow control eyes using a margin of 0.1 logMAR. The comparison between IC-8 IOL eyes and fellow eyes for mean monocular BCDVA (logMAR) will be performed using a t-test for non-inferiority at $\alpha = 0.05$ (one-sided). The null hypothesis is that the mean acuity for the IC-8 IOL eyes is inferior to the fellow eyes by 0.1 logMAR or more.

The alternative hypothesis is that the mean acuity for the IC-8 IOL eyes is inferior to the fellow eyes by less than 0.1 logMAR. Formally put as follows:

$$\begin{split} H_0: \mu_T - \mu_C \geq 0.1 \\ H_A: \mu_T - \mu_C < 0.1 \end{split}$$

Where μ_T is the mean logMAR acuity from the IC-8 eyes and μ_C is the mean acuity from the fellow eyes.

The statistical success criterion is when H_0 is rejected by a p-value less than 0.05, demonstrating the mean BCDVA from the IC-8 eyes is statistically non-inferior to the mean BCDVA from the control eyes using a margin of 0.1 logMAR.

b. The proportion of IC-8 eyes achieving BCDVA 0.3 logMAR or better is not less than the safety and performance endpoints (SPE) rate listed in ISO 11979-7:2014 Table B.3. The comparison between the proportion for the IC-8 eyes and the SPE rate for posterior chamber IOL (92.5%) will be performed using the exact test based on binomial distribution at $\alpha = 0.05$ (one-sided). The null hypothesis is that the proportion for the IC-8 eyes is not less than 92.5%. The alternative hypothesis is that the proportion for the IC-8 eyes is less than 92.5%. Formally put as follows:

> $H_0: p_T \ge 92.5\%$ $H_A: p_T < 92.5\%$

Where p_T is the proportion of IC-8 eyes achieving BCDVA 0.3 logMAR or better and 92.5% is the SPE rate for posterior chamber IOL.

The statistical success criterion is when H_0 is not rejected, i.e. the test result is a p-value greater than 0.05, demonstrating the proportion of IC-8 eyes achieving BCDVA 0.3 logMAR or better is not less than the SPE rate.

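### The co-primary DCIVA comparison between the two eyes of the same subjects is assigned a two-sample t-test; it should be a paired test, and with positive between-eye correlation the error costs power, not type I error

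*Combined protocol and SAP*

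**What the plan says.** Section 18.0 sets the frame for single-eye comparisons: "Monocular safety and effectiveness analyses will compare the IC-8 IOL eyes and the monofocal fellow eyes within the test group". Each test subject has one IC-8 eye and one monofocal eye, and under section 18.1 the ITT population contains only subjects implanted in both eyes. Every subject in the primary analysis therefore supplies a pair.

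For DCIVA at 6 months, section 18.2.1, item 4a, states that the comparison of IC-8 eyes with "fellow eyes in the test group for mean monocular DCIVA (logMAR) will be performed using a two-sample t-test", two-sided at 0.05, with a directional superiority hypothesis. The synopsis agrees: "mean values between the eyes implanted with the IC-8 IOL and the fellow eyes in the test arm will be compared using two-sample t-tests". The wording is thus repeated, not a single slip.

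Two other places bear on the point:

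- Section 18.3.1, item 1a, compares the same kind of eye pair on best-corrected distance acuity. It says that the comparison with "fellow eyes for mean monocular BCDVA (logMAR) will be performed using a t-test for non-inferiority", without saying whether the test is paired.
- Section 18.3.2 summarises contrast sensitivity in the same eyes through the mean between-eye difference, which is a within-subject analysis.

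All co-primary effectiveness endpoints must be met for the effectiveness claim. On the secondary astigmatism endpoint, section 18.0 adds that "this endpoint will only be tested when all co-primary effectiveness endpoints have been achieved".

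**The concern.** A two-sample t-test takes the variance of the mean difference as the sum of two independent variances. With paired eyes the true variance is smaller by twice the covariance. If the two eyes of one person are positively correlated, the unpaired standard error is too large, the p-value is too large and the confidence interval for the eye difference is too wide.

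Item 4a must be met for overall effectiveness and stands ahead of the astigmatism endpoint. A failure caused only by the wrong variance would cost both claims.

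The choice carries over to the 12-month repeat (18.2.4, item 3b) and to the propensity-stratified repeat (18.2.3). Section 18.4 also allows the corresponding non-parametric test if normality fails. Read literally, that would be a rank-sum test, not a signed-rank test.

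**Working it through.** **Inputs from the protocol.** Two-sided alpha 0.05 (18.2.1, item 4a); 300 test subjects completing one year, hence 300 pairs (7.0).

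**Inputs not in the text, assumed.** Equal SDs in the two eyes, 0.15 logMAR (range 0.10 to 0.20); between-eye correlation ρ of 0.3, 0.5 or 0.7; true differences of 0.02 to 0.10 logMAR. Section 18.4 places sample-size methods in the SAP, and the text reviewed gives no power calculation for item 4a.

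**Step 1: the plan's own arithmetic.** Section 7.0 allows 10% attrition and 5% disqualification.

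- Test arm: 300/(0.90 × 0.95) = 351, or 300/0.85 = 353, against 355 planned.
- Control arm: 100/(0.90 × 0.95) = 117, or 100/0.85 = 118, against 120 planned.

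The enrolment figures reproduce closely. The power behind the 300 cannot be checked.

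**Step 2: standard errors.**

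- SE used by the two-sample test = SD × √(2/n) = 0.15 × √(2/300) = 0.01225.
- True SE = SD × √(2(1 − ρ)/n) = 0.01025, 0.00866 or 0.00671 at ρ = 0.3, 0.5 or 0.7.
- Ratio = 1/√(1 − ρ) = 1.20, 1.41 or 1.83.

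**Step 3: actual size.** Two-sided size = 2 × [1 − Φ(1.96/√(1 − ρ))]. Only the tail favouring the IC-8 eye counts as success, so the false-success rate is half of this, against a nominal 2.5%.

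**Step 4: power.** Here d is the true difference and t the critical value (1.964 unpaired, 1.968 paired).

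- Unpaired: 1 − Φ((t × SE two-sample − d)/SE true).
- Paired: 1 − Φ(t − d/SE true).

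**Step 5: difference detectable with 90% power.**

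- Unpaired: t × SE two-sample + 1.2816 × SE true.
- Paired: (t + 1.2816) × SE true.

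Results for 300 pairs and SD 0.15:

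| | ρ = 0.3 | ρ = 0.5 | ρ = 0.7 |
|---|---|---|---|
| Two-sided size of the planned test | 1.9% | 0.56% | 0.035% |
| False-success rate (nominal 2.5%) | 0.96% | 0.28% | 0.02% |
| Power at 0.03, unpaired / paired | 0.72 / 0.83 | 0.75 / 0.93 | 0.81 / 0.99 |
| Power at 0.04, unpaired / paired | 0.94 / 0.97 | 0.97 / 1.00 | 0.99 / 1.00 |
| Power at 0.10, unpaired / paired | 1.00 / 1.00 | 1.00 / 1.00 | 1.00 / 1.00 |
| Detectable difference, unpaired / paired | 0.037 / 0.033 | 0.035 / 0.028 | 0.033 / 0.022 |

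The detectable difference is about 12%, 25% or 50% larger unpaired. At 90% power, 300 pairs analysed unpaired do the work of 242, 194 or 135 pairs analysed paired (exact noncentral t).

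**Step 6: sensitivity.**

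- At ρ = 0.5 and SD 0.20, power at 0.05 logMAR is 0.94 unpaired against 0.99 paired.
- With SDs of 0.10 and 0.20 in the two eyes and ρ = 0.5, the size is 1.1%.
- If ρ were negative the direction would reverse: size 6.2% at −0.1 and 7.4% at −0.2.

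**Step 7: simulation.** With 40,000 replicates of 300 pairs under the null, the unpaired test rejected in 1.83%, 0.54% and 0.03% of runs at ρ = 0.3, 0.5 and 0.7. The paired test rejected in 4.79%, 4.90% and 5.31%.

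**The case against.** The case for leaving it alone is that the practical consequence is close to nil.

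- **Size of effect.** At SD 0.15, unpaired power is already at least 0.94 at a true difference of 0.04 logMAR. The loss is concentrated at 0.02 to 0.04 logMAR. On the protocol's own scale (0.12 logMAR is 6 letters, so 0.02 is one letter) that is one to two letters.
- **Other hurdles.** Success also needs half of the IC-8 eyes at 0.2 logMAR or better and a mean depth of focus at least 0.5 D greater than in the fellow eyes. Nothing shows that item 4a would be the deciding test.
- **Planned power.** If the trial was sized as though the eyes were independent, positive correlation gives more power than planned in this range: at 0.03 logMAR and SD 0.15, 0.69 at ρ = 0 against 0.72 to 0.81. No shortfall against the sponsor's target is shown.
- **Condition.** Calling the test conservative presumes a correlation that the documents never state.

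All four points are fair. They limit the severity, and the conservatism must be stated as conditional on positive correlation. They do not make an independent-samples test right for paired eyes. The paired test keeps its level whatever the sign of the correlation, which is a further reason to prefer it. The SAP's detailed methods are not in the text reviewed; if they already specify pairing, section 18.2.1 and the synopsis contradict them and still need aligning.

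**Conclusion.** The concern holds: the test named for item 4a is wrong for the data. With positive between-eye correlation it does not inflate false success. It runs well below its stated level and gives up power that the design has already paid for. At SD 0.15 and ρ = 0.5, power at 0.03 logMAR falls from 0.93 to 0.75.

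The loss matters only for true differences of about 0.02 to 0.04 logMAR, or up to about 0.05 if the SD is 0.20. It is negligible at 0.10. This is a method correction that should be made, not a threat to the trial's conclusion. The sizes rest on assumed SDs, assumed correlations and 300 complete pairs; the direction rests only on positive correlation.

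The BCDVA item in 18.3.1 is an ambiguity, not a stated error.

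**What to change.** 1. In 18.2.1, item 4a, and in the synopsis, replace the two-sample t-test for DCIVA with a paired t-test on the within-subject difference (IC-8 eye minus fellow eye). Hypotheses and alpha stay as they are. Name the signed-rank test as the non-parametric fallback under 18.4.
2. For analyses with incomplete pairs, such as the non-imputed per-protocol analysis, specify a mixed model with a subject effect. With complete pairs it reproduces the paired comparison; with incomplete pairs it adds a missing-data assumption, which should be stated.
3. As a clarification, say in 18.3.1, item 1a, that the BCDVA t-test is paired, with the same provision for incomplete pairs. These can arise because the safety population includes failed IC-8 implantations and section 18.1 says "Safety analyses will only include available data at the time of analysis (i.e., no data imputation").
4. Keep the two-sample form for the supportive analysis in 18.2.4, item 3a, in which the monocular endpoints "will be repeated by comparing IC-8 IOL eyes to the second eyes in the control group". Those eyes come from different subjects.
5. Align the SAP if it differs.

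The cost is wording only, with no new data or subjects. Make the change before outcome data are seen, so that moving to the more powerful test cannot look data-driven.
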